#### 9.4.4 Other Analyses

**Analysis of the Primary Biologic Endpoint (which is a secondary endpoint of the trial):** Patients who do or do not exhibit proposed relative differences in the ratio of *IL6/IL23/IL17* to *Foxp3/TGF $\beta$*  at baseline (suggesting a classic lupus T Cell signaling imbalance that might be reversed by Abatacept) will be compared for proportion of responders in treatment vs placebo group. Patients identified at baseline with TH17 hi with  $>/= 50\%$  change towards normal after treatment will be compared separately for response rates. These endpoints will be described in terms of confidence intervals based on the primary clinical endpoint. Similar analysis will be done for patients with high vs low BlyS or high vs low interferon alpha inducible gene expression.

**Analysis of Secondary and Exploratory Biologic Endpoints:** Mean or median change in cytokine, immunoglobulin and gene expression levels will be explored. Bucketing of baseline profiles might be used to develop propensity scores suitable for a simplified refinement of the primary biologic endpoint by combining variables that might either increase or decrease the likelihood of response. Given the complex array of data we are likely to generate, principal component analysis can be applied to identify directions (principal components) along which the variation of the data is maximal.

It should, however be pointed out that even if statistical significance is not met, a large enough effect size in the primary endpoint of a small pilot study this size might still be encouraging enough to continue development of this drug, particularly if biologic subanalyses provide insight into the responder profile.

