Statistics:	
Primary Clinical Endpoint: proportion of patients on abatacept vs placebo who meet BICLA criteria at month 6 compared to baseline by Ch sq or Fishers Exact Test. Powering of the Study Based on the Primary Endpoint: Powering assumptions assume response rates ranging from 35-50%. based on data from patients with lupus arthritis in the Phase II abatacept study, where physicians rated 40% of the patients treated with abatacept as having “no flare.” Using the BICLA, response rates in the epratuzumab EMBLEM trial was also about 40% at optimal dosing, therefore this range seems applicable. Data from the BOLD study confirm that there should be a near zero (2.4%) percent response by BICLA at six months in the placebo group in a study with background IS withdrawal. Therefore our assumption of at least 5% response in the placebo group in an identical trial design is reasonable and with range of 40-50% response in the treatment group power > 0.8 to detect a difference. Exploratory Analysis of Primary Endpoint: To address potential confounders in a small study a propensity score will be applied to simplify multiple variables into one variable.
 
Secondary Clinical Endpoints: BICLA and SRI at each month. Mean SLEDAI, BILAG, CLASI, PGA, DIAL and PRO by paired T test. Main Biologic Endpoint: Patients who do or do not exhibit proposed relative differences in the ratio of IL6/IL23/IL17 to Foxp3/TGF<math>\beta</math> (suggesting T Cell signaling imbalance) or aberrant ErK phosphorylation (indicating abnormal signaling through B Cell receptor) at baseline will be compared for proportion of responders in treatment vs placebo group. Patients identified at baseline with high TH17 signal or ErK phosphorylation with <math>\geq</math> 50% change towards healthy mean (+2SD) after treatment will be compared separately for response rates. These endpoints will be described in terms of confidence intervals based on the primary clinical endpoint. Analysis of Secondary and Exploratory Biologic Endpoints will include mean (or median) change in cytokine, immunoglobulin and gene expression levels explored based on known patterns of overexpression in SLE. Bucketing of baseline profiles might be used to develop propensity scores suitable for a simplified refinement of the primary biologic endpoint by combining variables that might either increase or decrease the likelihood of response. Given the complex array of data we are likely to generate, principal component analysis can be applied to these exploratory studies to identify directions (principal components) along which the variation of the data is maximal.

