The study population will include patients between the ages of 18 and 70 who meet a minimum of 4 1997 revised ACR criteria for SLE and who present with a minimum of 3 tender and 3 swollen joints attributable to lupus arthritis. Patients may have other active manifestations of SLE, and, in the opinion of the investigator, they must be sick enough for intention to treat with a biologic and stable enough for this trial design, which includes withdrawal of any background immune suppressants, to be appropriate.

This study will enroll patients until 60 have completed the protocol through at least the six month point. Randomization will be 1:1 to abatacept or placebo. Approximately 30 patients are expected to complete each arm. At each visit history, physical, and blood tests appropriate to complete the outcome measures will be performed, and adverse event reporting and medication updates will be performed.

Subjects may continue to take nonsteroidal anti-inflammatory medications (including *prn* NSAIDS) and up to 20 mg prednisone (or oral steroid equivalent) daily during the study although steroids will be tapered as tolerated. If the patient is taking an immune suppressant (e.g. antimalarials, mycophenolate mofetil, azathioprine, leflunomide, methotrexate, a calcineurin inhibitor or belimumab) at screening, this must be stopped prior to or on the day of the baseline visit. Patients can elect to receive one or more depomedrol injection(s) up to a total of 320 mg total at the time of the screening visit and/or up to and including the Month 2 visit. Daily oral steroids will be tapered as tolerated if and when the patient begins to improve.

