## **6.4.2 Secondary Efficacy Assessments**

***All of the individual components of the BICLA will be assessed in different ways as secondary endpoints. These will include:***

1. BICLA response at each month
2. SRI 4 and 5: Response is defined at an endpoint date (EOS and each month vs baseline) The SRI endpoint (7) is defined as a 4 (or 5) point drop in SLEDAI compared to baseline without an increase in BILAG or 10% worsening by PGA.
3. Tender and swollen joint counts (to be analyzed separately and as composite score)
4. Change in SLEDAI scores (EOS and each month vs baseline)
5. Change in PGA scores (EOS and each month vs baseline)
6. Change in BILAG numerical scores (Addition of organ scores where each A=12, B=8, C=1 and D or E=0).
7. Musculoskeletal BILAG response (% with one grade drop and % who reach C or lower)
8. Responder Analysis using the primary endpoint and assessing baseline evidence of (and changes in) a panel of markers selected to identify high levels of IL6/TH17 signalling, and/or B Cell signaling (Erk/Blys). All methods proposed have been previously standardized and are currently available in our laboratory as reviewed above. These will be re-standardized for the current study.

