### 9.1 Sample Size Determination

**Sample Size** Based on data from the BOLD study confirming the low response rates in a placebo group at 6 months in a study design identical to the structure of this protocol (1/41 patients or 2.4% met the BICLA response at 6 months in that study) and based on the assumption that the response rate to abatacept using this design and these endpoints would be at least equivalent to what was found in the Phase II Epratuzumab or Phase III BLISS studies (roughly 40-50% response). The sample size was optimized at 60 patients in a 1:1 randomization scheme with alpha = 0.5 and desired power 0.8.

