### 9.2 Populations for Analyses

**The subject population** As further detailed in the inclusion and exclusion criteria will consist of consecutive consenting lupus patients between ages 18 and 70 who have active polyarticular arthritis characterized by 3 or more tender and 3 or more swollen joints at the screening visit meeting the BILAG 2004 criteria for  $\geq$  B disease (+/- additional evidence of disease activity in other organs).

**The clinical justification** is based on the combination of unmet need in treating a significant, potentially disabling illness, while ensuring a healthy enough population to justify the risks of studying a biologic treatment vs placebo.

**Power Analysis:** Chi Sq or the Fisher's exact test will be used for analysis. The table below has been powered on the assumption that the placebo group will have a result similar to (or even a bit more responsive than) that found in the BOLD study (which was the test prototype for this protocol to determine the safety and feasibility of the statistical assumptions for the placebo study). Data from the BOLD study confirm that there should be a near zero (2.4%) percent response by BICLA at six months in the placebo group in a study with background IS withdrawal. Therefore our assumption of at least 5% response in the placebo group in an identical trial design is reasonable. The second assumption is that the treatment group will have a response rate somewhere between those found in the epratuzumab (by BICLA) and BLISS phase II/III (by SRI) biologic studies e.g. a predicted response rate between 35 and 50%. The most important basis for this assumption, however are the data from patients with lupus arthritis in the Phase II abatacept study, where physicians rated 40% of

the patients treated with abatacept as having “no flare” after baseline. Therefore this expected range by BICLA seems reasonable. (please see power analysis table below which is based on powering the primary endpoint at a range of expected response rates in treatment and placebo groups with a sample size of 60 patients, alpha=0.05).

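### The biomarker-response analyses group continuous baseline markers at cuts that are never given, which loses precision and leaves the cut open to choice after the data are seen

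*Combined protocol and SAP*

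**What the plan says.** Section 9.4.4 defines the analysis of the primary biologic endpoint by groups: "Patients who do or do not exhibit proposed relative differences in the ratio of" IL6/IL23/IL17 to Foxp3/TGFβ are compared for responder proportions on treatment and placebo. The Statistics row of the synopsis adds aberrant ERK phosphorylation and uses the same comparison: both markers "at baseline will be compared for proportion of responders in treatment vs placebo group". Section 9.4.4 then extends the method: "Similar analysis will be done for patients with high vs low BlyS or high vs low interferon alpha inducible gene expression". Section 6.4.2, item 8, lists a responder analysis on "a panel of markers selected to identify high levels of IL6/TH17 signalling, and/or B Cell signaling".

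Section 6.4.2 describes the underlying measurements as gene expression levels, ERK phosphorylation after stimulation, and measured BLyS. None is naturally binary. No section gives a numeric baseline value that separates high from low. The healthy mean (+2SD) in the synopsis is attached to change after treatment. Results are to be described by confidence intervals; no test, alpha or power is stated for this endpoint.

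**The concern.** Grouping a continuous marker treats patients just either side of the cut as different and all patients on one side as alike. With about 30 treated patients and 12-15 responders among them (30 × 0.40 to 30 × 0.50), there is little information to spare. An unstated cut can also be settled after response is known, and then neither the estimate nor its interval means what it appears to mean.

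The stakes are real although the endpoint is secondary. Section 2.2 wants these data to help select patients for later trials. The close of 9.4.4 says development might continue without a significant primary result, particularly if the biologic sub-analyses shed light on who responds.

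**Working it through.** **The plan's own figure.** The only power stated is for the primary BICLA comparison. With 30 per arm, two-sided 0.05 and a continuity correction, the effective size per arm is n′ = n − 2/d + 1/(n·d²), and power = Φ{[d√n′ − 1.96√(2p̄q̄)] / √(p₁q₁ + p₂q₂)}. For 40% vs 5%, d = 0.35 and n′ = 30 − 5.71 + 0.27 = 24.56. Then (1.734 − 1.158)/0.536 = 1.08, giving 0.859 against the stated 0.86. All seven columns come to 0.848, 0.869, 0.897, 0.804, 0.859, 0.749 and 0.830, against 0.84, 0.86, 0.89, 0.80, 0.86, 0.77 and 0.84. The table is sound, but it says nothing about the markers.

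**Inputs from the documents.** Section 9.1: "The sample size was optimized at 60 patients in a 1:1 randomization scheme". Section 4.1: "Approximately 30 patients are expected to complete each arm". Section 9.2: "a predicted response rate between 35 and 50" percent on abatacept, and at least 5% on placebo. Alpha is from 9.2: "with a sample size of 60 patients, alpha=0.05" (9.1 prints 0.5, which conflicts with 9.2 and the power table; 0.05 is used here).

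**Assumed, because the plan is silent.** Two-sided testing, a normally distributed (log) marker, a logistic relation to response, the odds ratio (OR) per SD, and the cut.

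**Within the abatacept arm (30 patients, median split), by simulation.** Each cell gives power for the continuous marker, then for chi-square on the split.

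| OR per SD | Likelihood-ratio test, 40% response | Likelihood-ratio test, 50% response | Firth logistic, 40-50% response |
|---|---|---|---|
| 1.5 | 0.198 / 0.129 | 0.198 / 0.120 | 0.16-0.18 / 0.12 |
| 2 | 0.421 / 0.265 | 0.435 / 0.273 | 0.36-0.37 / 0.25-0.26 |
| 2.5 | 0.618 / 0.402 | 0.622 / 0.400 | not run |
| 2.7 | not run | not run | 0.63-0.65 / 0.44-0.47 |
| 3 | 0.728 / 0.499 | 0.749 / 0.512 | not run |
| 4 | 0.869 / 0.658 | 0.886 / 0.673 | 0.84-0.85 / 0.66-0.67 |

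Null rejection in the Firth runs was 0.04-0.06. Across the continuous tests tried (likelihood-ratio, t, rank, Firth), the loss at OR 2-4 is about 10-24 points, and at OR 1.5 about 3-8.

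**Hand check.** A median split of a normal marker keeps 2/π = 64% efficiency. With 12 responders and 18 non-responders differing by δ SD, power ≈ Φ(δ√(12·18/30) − 1.96). At δ = 0.8 this is Φ(2.147 − 1.96) = 0.574. Multiplying the 7.2 under the root by 2/π gives Φ(1.713 − 1.96) = 0.402, a loss of 17 points. Over δ = 0.6-1.2 the loss is 11-19 points.

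**Dependence on the cut and test.** At 50% response and OR 2-4, a cut that makes about 84% of patients high costs 25-45 points (likelihood-ratio against chi-square). Fisher's exact test on a median split costs 24-38 points against the t-test.

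**Marker-by-arm contrast (30 + 30).** On the logistic scale at 40% vs 5%, power at OR 2, 3 and 4 is 0.126, 0.213 and 0.257 continuous, against 0.089, 0.147 and 0.206 split: a loss of 4-7 points. Over other rate pairs, up to 50% vs 20%, the loss is 3-18 points. Power is low because the placebo arm expects only 30 × 0.05 = 1.5 responders. The chance of 0 or 1 is 0.95³⁰ + 30·0.05·0.95²⁹ = 0.55; at the 2.4% seen in BOLD it is 0.84. On the risk-difference scale (40% against a flat 5% on placebo, linear model with HC3 errors), power is 0.38 vs 0.23 at OR 2 and 0.79 vs 0.57 at OR 4.

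**In interval terms.** Suppose the high half has 8/15 responders on abatacept and 1/15 on placebo, and the low half 4/15 and 1/15 (12/30 = 40% on abatacept overall). The Newcombe 95% intervals for the difference are 14 to 69 points and −8 to 46 points. They overlap widely.

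**The case against.** The endpoint is secondary, hypothesis-generating and reported by confidence intervals, so power is not its stated criterion. That stands: the cost is better thought of as lost precision, with power as one measure of it.

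The plan compares treatment with placebo within marker groups, so a loss computed inside the abatacept arm describes a different question. That also stands, and the two are kept apart above. A reader might infer that the larger loss applies to the planned contrast; on the logistic scale it does not.

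Grouping has a purpose. The hypothesis concerns an aberrant state, and patient selection eventually needs a rule. If response truly jumps at the cut, the split wins: with 60% vs 20% response either side of a median cut, power is 0.62 split against 0.48 on the full scale. This is a fair reason to keep a high/low display, but not to make an unspecified cut the only analysis.

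One might read the healthy mean (+2SD) as an implied baseline cut. The synopsis uses it only as the target for change after treatment, and 9.4.4 does not repeat it.

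**Conclusion.** The point holds as a precision and prespecification problem. Baseline markers measured on continuous scales are related to response only through groups whose cuts are not stated.

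Under the listed assumptions (30 abatacept patients, 40-50% response, normal marker, OR 2-4 per SD, median split, chi-square), the split costs roughly 10-24 points of power within the abatacept arm, and 3-8 points at OR 1.5. For the marker-by-arm contrast on the logistic scale it costs about 3-18 points, and 4-7 at 40% vs 5%. Section 1.2 plans the relevant gene-expression array in a subset of patients, so the lead T-cell marker may have fewer than 30 treated patients and less power than shown.

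Three stronger readings are not supported. A fixed power loss cannot be quoted, because the documents give no marker effect, cut or test. Most of the information is not lost, since a median split of a normal marker keeps about 64% efficiency. BLyS and the interferon signature are not part of the main biologic endpoint: Section 6.4.2 defines it by the T-cell ratio and B-cell activation (ERK), and 9.4.4 adds the other two as a similar analysis.

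**What to change.** In 9.4.4 and the synopsis:

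- Make the baseline marker on its continuous scale (log or rank, stated in advance) the main analysis for the T-cell ratio and ERK phosphorylation, and likewise for BLyS and the interferon score.
- Report the abatacept-arm odds ratio per SD for BICLA response at Month 6, with its 95% interval, from a Firth-penalised logistic model. State how many patients have each marker measured.
- Report the marker-by-arm contrast descriptively with its interval, preferably on the risk-difference scale. Do not rely on a separate placebo-arm slope, since 0 or 1 placebo responders is likely.
- Keep responder proportions by high/low group and arm as a secondary display, at a cut fixed before unblinding.

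The cost is protocol and SAP wording and a little analysis time, with no new samples or patients. The downside is lower sensitivity if response truly jumps at one threshold; the retained table would still show that pattern.

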### 10. Study Management

**10.1 Compliance with the Protocol:** All protocol deviations or violations will be collected and reported to the IRB and DSMB. Compliance with the protocol is a high priority and we will hire a professional study monitor to ensure compliance and accuracy in data collection.

**10.1.1 Compliance with the Protocol and Protocol Revisions:** *The study shall be conducted as described in this approved protocol. All revisions to the protocol must be discussed with, and be prepared by, BMS. The investigator should not implement any deviation or change to the protocol without prior review and documented approval/favorable opinion from the IRB/IEC of an amendment, except where necessary to eliminate an immediate hazard(s) to study subjects.*

If a deviation or change to a protocol is implemented to eliminate an immediate hazard(s) prior to obtaining IRB/IEC approval/favorable opinion, as soon as possible the deviation or change will be submitted to:

- IRB/IEC for review and approval/favorable opinion
- Bristol-Myers Squibb
- Regulatory Authority(ies), if required by local regulations

Documentation of approval signed by the chairperson or designee of the IRB(s)/IEC(s) must be sent to BMS.

If an amendment substantially alters the study design or increases the potential risk to the subject: (1) the consent form must be revised and submitted to the IRB(s)/IEC(s) for review and approval/favorable opinion; (2) the revised form must be used to obtain consent from subjects currently enrolled in the study if they are affected by the amendment; and (3) the new form must be used to obtain consent from new subjects prior to enrollment.

If the revision is an administrative letter, investigators must inform their IRB(s)/IEC(s).

## **10.2 Records Retention**

**10.2.1 Records Retention:** The investigator must retain all study records and source documents for the maximum period required by applicable regulations and guidelines, or institution procedures, or for the period specified by BMS, whichever is longer. This includes a minimum of fifteen years after the end of the study as per usual practice in industry supported trials. If the investigator withdraws from the study (eg, relocation, retirement), the records shall be transferred to a mutually agreed upon designee (eg, another investigator, IRB). Notice of such transfer will be given in writing to BMS.

**10.2.2 Study Drug Records:** It is the responsibility of the investigator to ensure that a current disposition record of investigational product (those supplied by the BMS) is maintained at each study site where study drug and noninvestigational product(s) is/are inventoried and dispensed. In this case there will be one site at the Oklahoma Medical Research Foundation. Records and logs will be kept by our unblended pharmacy administrator within the locked pharmacy space and must comply with applicable regulations and guidelines and should include:

- amount received and placed in storage area
- amount currently in storage area
- label ID number or batch number
- amount dispensed to and returned by each subject, including unique subject identifiers
- amount transferred to another area/site for dispensing or storage
- non-study disposition (eg, lost, wasted)
- amount destroyed at study site, if applicable
- amount returned to the BMS
- retain samples for bioavailability/bioequivalence, if applicable
- dates and initials of person responsible for Investigational Product (IP) dispensing/accountability, as per the Delegation of Authority Form.

**10.3 Destruction of Investigational Product:** If the study drugs are to be destroyed on site, it is the investigator's responsibility to ensure that arrangements have been made for disposal, and that procedures for proper disposal have been established according to applicable regulations, guidelines, and institutional procedures. Records of the disposal must be maintained.

## 11 GLOSSARY OF TERMS

Term	Definition
Adverse Reaction	An adverse event that is considered by either the investigator or the sponsor to be related to the investigational product
Expedited Safety Report	Rapid notification to investigators of all SAEs that are suspected (related to the investigational product) and unexpected (ie, not previously described in the Investigator Brochure), or that could be associated with the study procedures.
SUSAR	Suspected, Unexpected, Serious Adverse Reaction as termed by the European Clinical Trial Directive (2001/20/EC).
Unexpected Adverse Reaction	An adverse reaction, the nature or severity of which is not consistent with the applicable product information (eg, Investigator Brochure for an unapproved investigational product)

## 12 LIST OF ABBREVIATIONS

AB	Antibody
ACR	American College of Rheumatology
AE	Adverse event
ALT	Alanine Transaminase
APC	Antigen-Presenting Cell
ARA	American Rheumatology Association
AST	Aspartate Transaminase
BCG	Bacillus Calmette-Guérin
BICLA	BILAG-based Combined Lupus Assessment
BILAG	British Isles Lupus Assessment Group
BMS	Bristol-Myers Squibb
BUN	Blood Urea Nitrogen
CBC	Complete Blood Count
CDC-ACID	Centers for Disease Control and Prevention Advisory Committee on Immunization Practices
CFR	Code of Federal Regulations
CI	Confidence Interval
CLASI	Cutaneous Lupus Erythematosus Disease Area and Severity Index
CMV	Cytomegalovirus
CRF	Case Report Forms
CRP	C-Reactive Protein
CTLA	Cytotoxic T-Lymphocyte Associated
CXR	Chest X-Ray
DIAL	Directed Integrated Assessment of Lupus
DMARD	Disease-Modifying Antirheumatic Drug
DNA	Deoxyribonucleic Acid
D5W	Dextrose (5%) in Water
EC	European Commission
ESR	Expedited Safety Report
EULAR	European League Against Rheumatism
FDA	Food and Drug Administration
FSH	Follicle-Stimulating Hormone
GCP	Good Clinical Practice
GGT	Gamma-Glutamyltransferase
GM-CSF	Granulocyte Macrophage Colony-Stimulating Factor

HCG	Human Chorionic Gonadotropin
HIV	Human Immunodeficiency Virus
HLA	Histocompatibility Leukocyte Antigen
HRT	Hormone Replacement Therapy
IB	Investigator Brochure
ICH	International Conference on Harmonisation
IEC	Independent Ethics Committee
IL	Interleukin
IND	Investigational New Drug (Application)
IRB	Independent Review Board
IST	Investigator-Sponsored Trial
IU	International Unit
IV	Intravenous
JRA	Juvenile Rheumatoid Arthritis
MHC	Major Histocompatibility Complex
MRI	Magnetic Resonance Imaging
NPV	Negative Predictive Value
NS	Normal Saline
NSAE	Non-Serious Adverse Event
NSAID	Non-Steroidal Anti-inflammatory Drug
OA	Osteoarthritis
PCR	Polymerase Chain Reaction
PPD	Purified Protein Derivative
PPV	Positive Predictive Value
PVC	Polyvinylchloride
RA	Rheumatoid Arthritis
RF	Rheumatoid Factor
SAE	Serious Adverse Event
Se	Sensitivity
SLE	Systemic Lupus Erythematosus
SLEDAI	SLE Disease Activity Index
SRI	SLE Responder Index
SmPC	Summary of Product Characteristics
Sp	Specificity
SUSAR	Suspected Unexpected Serious Adverse Reaction
SWFI	Sterile Water For Injection

TB	Tuberculosis
TNF	Tumor Necrosis Factor
ULN	Upper Level of Normal
VAS	Visual Analog Scale
WBC	White Blood Cell
WOCBP	Women of Childbearing Potential

